## **Baseline, 6 week, 3 month and 6 month Data Collection.**

### **Intervention group**

Data from baseline testing plus additional strength test and POC will be entered in Progress Note.

6 week testing will be entered in the last session for the Intervention group (discharge information in last daily documentation note as would be in standard PT practice.)

3 month booster session will be reported in Note by PT/TR titled Intervention Booster Session. No data will be entered into E Chart.

6 month testing- Note will be entered by PT/TR documenting they participated in testing for LIFT study. No data entered into E Chart.

### **CONTROL group**

Initial, 6 week, 3 and 6month testing data will not be entered into eChart. A note will be entered by PT/TR documenting that they participated in testing for LIFT study.

## **OCCUPTATIONAL THERAPY**

### **Home Safety Evaluations**

The provider conducting home safety evaluations will complete the HOME- FAST form (Appendix E) and assess mobility in the home, and identify environmental obstacles and hazards. Recommendations will be written and shared with participant. Both forms will be scanned into the medical chart. Time Spent with Patient ad hoc outpatient form will be used and 0 (zero) will be entered under Ther Act for time and units with patient.

### **Therapeutic Recreation Services (both groups)**

INTERVENTION GROUP: The therapeutic recreation therapist will document using Recreation Therapy Progress Note. As per usual care, there will be no charges.

CONTROL GROUP – The therapeutic recreation therapist will track attendance and there will not be any additional documentation.

## **Training**

### **MAHHC Outpatient Physical Therapists**

LIFT investigators will provide information to the Mt Ascutney physical therapists who will be identifying eligible patients during a one-hour session. Information about the study and the eligibility criteria will be provided. The physical therapists will be trained in how to use the eligibility form, and where to submit it (Eligibility Form: Appendix G; Training Form for Outpatient Therapists: Appendix H). Printed copies of the Participant Study Summary will be provided.

### **MAHHC Secretaries**

The MAHHC secretaries will fax the eligibility forms and refer calls about the study to [name]. A contact list for study investigators will be provided to the secretaries.

## **LIFT Research staff**

Each member of the research staff will undergo Human Subjects protection training via CITI courses through Boston University. In addition, they will attend a 2 hour study-specific training in LIFT procedures conducted by the principal and co-investigator. A one hour retraining session will occur prior to the 2nd and/or 3rd class session if more than 6 weeks has elapsed between sessions. This content will include study specific human subjects protection, study procedures, data collection, adverse event reporting, including reporting if assessor is unblinded to study assignment. In addition to this training, members of the research team conducting the exercise class, the behavioral component (Goal-setting and Peer-coaching), the control sessions, and data collection (including adverse events) will undergo component-specific study training

**Exercise Component:** Providers conducting the group exercise component will complete certification in the Otago program, and undergo 1 hour training in study-specific content and progression of the group class, activity monitor use, and study documentation. See Appendix I: Training documentation form and Appendix L: Training for Exercise Component.

**Data Collection:** The data collectors will be trained in administration of the study questionnaires, and in the physical performance tests. See Appendix I: Training documentation form; Appendix J: Physical Performance Test Training Log; Appendix K: Physical Performance Tests: Strength, Balance, and Walking Assessments

## **LIFT Study subjects**

### **Identification**

Outpatient physical therapists will identify potentially eligible patients using the Eligibility form provided (Appendix G). If the patient is eligible, the physical therapist will inform the patient of the study and ask if they are interested in hearing more about it. They will provide the study summary to the patient, provide contact information on the Eligibility form, and let the patient know that study staff will contact them. They will submit the forms to the outpatient PT secretary, who will contact [name] to alert her that an eligible participant has been identified.

### **Enrollment**

Study staff will call the patient to provide information on the study, answer questions and set up a time to enroll, likely before or after the next physical therapy session. At that session, study staff will provide specific information on the class meeting times and commitment, and clarify that the start date is to be determined when all 16 participants have been enrolled. She will obtain written, informed consent, and let the participant know that study staff will call them about when the program will begin. [name] will complete the Master Key document (Appendix M), assigning the participant a study identification number (study ID). The study ID will be used to identify the participant in the consent form and data collection forms.

### **Randomization**

[name] will insert the study ID, age and sex into the Randomization Spreadsheet (Appendix N). When 16 IDs are listed on the sheet, she will email to the blinded study analyst, who will use a computer algorithm to randomly assign the participants to study condition, blocked by age and sex. The analyst will send the spreadsheet back to [name] with the assignments.

### **Notification**

Unblinded study staff will contact the patients to notify them of their study group assignment, the day and time of the baseline data collection, and the schedule of the group sessions. Study staff

will inform the participants that at the baseline data collection, the data collector will not know their study group and should not be informed.

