### **Preliminary Efficacy Data**

#### **Baseline Data Collection (See Appendix R)**

Both Groups	
Performance-based Measures	Self-report
4-stage Balance	demographics
TUG	LLFDI community mobility short form
30-second Chair Stand	FES-I
DGI	ABC-6
	Barriers Self-Efficacy
	Technology Use Questionnaire
	Get up from floor
	New/change in health status
	Recent fall(s) and mobility questions
	Home Assessment Questions

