## **Baseline Data Collection and Orientation**

### **LIFT Intervention group**

Within 2 weeks of the start of the program, the participants will be invited to come to a baseline Data Collection and Program Orientation session. Blinded research staff will provide questionnaires, conduct the physical tests, and complete the Baseline Data Collection Form. The Intervention and Control groups will be invited to separate Data Collection times or rooms in groups of 4. For example, 4 of the Intervention participants will be scheduled for 10:00am on Thursday. They will be shown into one room. The blinded research staff ([name]) will be informed of the room and time, but not the assignment of the group. She will inform the participants that she must not know their assignment. She will instruct the participants to complete the questionnaires, and offer to clarify as needed. While participants are completing the questionnaires, she will conduct the TUG, 30 second chair stand, 4-stage balance test and Dynamic Gait Index (10 minutes) individually. When participants have completed the questionnaires and physical tests, The Data Collector ([name]) will release them to unblinded study staff ([name]), who will bring the participants to the appropriate location for their separate orientation sessions. She will also deliver the physical test results to the Intervention group instructor ([name]) to inform the Orientation session. The orientation will consist of an explanation of the overall structure of the class, provision of the Participant Binder and the activity monitors, and ascertaining the starting weight for strength training. Instruction will be provided on use of the monitors. Participants will be asked to wear the monitors daily and to record their steps in their Action Plan (Appendix B) until the first program session to establish their baseline walking activity. The Action Plan will also be used to track daily symptoms and falls on a daily basis.

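### Participants are told their arm before they answer the baseline questionnaires; disclosing it at the end of that visit would keep arm knowledge out of those data, provided no earlier PT step reveals it

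*Combined protocol and SAP*

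**What the plan says.** Under Randomization, arms are assigned once 16 participants are listed. Documentation of PT and OT Services places baseline testing after that step. Under Notification, "Unblinded study staff will contact the patients to notify them of their study group assignment, the day and time of the baseline data collection"; the same contact gives the session schedule. Participants are also told that "at the baseline data collection, the data collector will not know their study group and should not be informed".

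Under Baseline Data Collection and Orientation, the visit takes place "Within 2 weeks of the start of the program". The data collector "will be informed of the room and time, but not the assignment of the group", and the section adds: "She will inform the participants that she must not know their assignment". Participants fill in the questionnaires themselves. The self-report column of the baseline table includes LLFDI, FES-I, ABC-6, "Barriers Self-Efficacy", a get-up-from-floor item, and questions on recent falls and mobility. "When participants have completed the questionnaires and physical tests", they pass to an unblinded staff member, "who will bring the participants to the appropriate location for their separate orientation sessions".

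The Statistical Analysis Plan reports pretest means and SDs, compares the groups at baseline, and uses baseline fall rates and other variables to size a later trial. At each post-test it fits an ANCOVA adjusting for the pretest. It also says that the study is not powered for between-group differences.

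**The concern.** On a self-completed scale the respondent is the rater, so an unaware data collector does not keep arm knowledge out of the answers. Someone just told that they will join a program aimed at exercise self-efficacy may answer confidence questions differently from someone told that they will attend the control class. The documents do not show that this happens, but the sequence allows it. They list no earlier measurement of these items: the eligibility form and the earlier outpatient PT evaluation are not shown to contain them.

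Three things are exposed: the descriptive baseline, the baseline values carried into planning, and, for scales repeated at follow-up, the ANCOVA covariate. Pretest adjustment cannot repair a pretest that is itself affected. Enrollment, attendance, safety counts and exercise adherence (which has no listed baseline value) are not affected by this route. The four performance tests are done by a blinded assessor and are outside this point.

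**Working it through.** The plan gives no figure to reproduce, so the check has two parts: the order of events, and an illustration of what that order could do.

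**Order.** Enrollment, randomization in waves of 16, one contact giving arm and baseline appointment, self-completed questionnaires and tests, handover to separate orientations. The arm is known before the questionnaires.

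**Inputs.** From the documents: 48 patients (Specific Aims), in 3 waves of 16 (3 x 16 = 48). The program summary splits the intervention class into two groups of 4, so 8 per wave and 3 x 8 = 24 per arm; the allocation ratio itself is not stated. Assumed: pre-post slope b = 0.5 to 0.8; between-arm shift from arm knowledge at baseline d1 = 0.1 to 0.3 SD; follow-up shift d2 = k x d1; no drop-out and no class clustering.

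**Formula.** With the current order, the bias of the ANCOVA treatment coefficient is d2 - b x d1 = (k - b) x d1. With disclosure after baseline, the d1 term disappears and the bias is d2 = k x d1.

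| Share of shift persisting (k) | Current order (SD) | Disclosure after baseline (SD) |
|---|---|---|
| 0 | -0.24 to -0.05 | 0 |
| 0.5 | -0.09 to 0.00 | +0.05 to +0.15 |
| 1 | +0.02 to +0.15 | +0.10 to +0.30 |

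**Break-even.** The two errors are equal in size when d2 = b x d1 / 2, that is k = b/2: 0.25, 0.35 and 0.40 for b = 0.5, 0.7 and 0.8. For a positive d1, later disclosure gives the smaller net error only below that share, or when d2 has the opposite sign. With no shift, neither order is biased.

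**Simulation check** (b = 0.7, 24 per arm, no true effect, 20,000 runs, d1 = 0.2). Mean estimates for the current order against later disclosure: d2 = 0.07, -0.069 against +0.069; d2 = 0.1, -0.039 against +0.103; d2 = 0.2, +0.059 against +0.200. With d2 = 0, the current order gives -0.141. These agree with the formula.

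**Scale.** SE = sqrt((2/n) x (1 - b^2)). At n = 24 this is 0.250, 0.206 and 0.173 SD for b = 0.5, 0.7 and 0.8; at n = 20 it is 0.274, 0.226 and 0.190. Class clustering would normally raise it.

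**Could the planned baseline comparison detect a shift?** Its SE is sqrt(2/24) = 0.289 SD. Two-sided 5% power for shifts of 0.1, 0.2 and 0.3 SD is 6%, 10% and 17%. A difference that did appear could not be told from chance imbalance.

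**The case against.** The strongest objection is that participants know their arm at every follow-up. If the shift persists, the affected pretest partly cancels it, and removing only the baseline part can leave a larger net error. This happens in two of the three rows above. If k is spread evenly over 0 to 1 and b evenly over 0.5 to 0.8, later disclosure gives the smaller error in a share equal to the mean of b/2, which is 0.65/2 = 0.325, or about one third. For the ANCOVA estimate this objection stands. It does not touch the pretest means and SDs or the baseline comparison, where nothing cancels. Cancellation also depends on two unknown shifts and an unknown slope, so it cannot be relied on.

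Second, rewording the call may not be enough. The PT documentation section has intervention participants discharged from outpatient PT, while controls may continue it, and does not say when this happens relative to baseline. If it comes first, it can reveal the arm. This stands and makes the benefit conditional.

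Third, the cost may fall on Aim 1. Participants would learn their own schedule only at a visit held at most two weeks before classes that begin twice weekly, with no minimum gap stated. Attendance and completion could suffer slightly. This stands in part: the Enrollment section has class times discussed at consent, though it does not say which schedule will be theirs.

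**Conclusion.** The point holds as a cheap improvement with low stakes. Confidence is high for the sequence and low for the size of any bias. The assured gain, once nothing else reveals the arm first, is baseline self-report data that arm knowledge cannot have altered. It covers the get-up-from-floor item and the recent-falls and mobility questions as well as the four scales.

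A reader might infer more, and the documents do not support it:

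- **That the efficacy estimates are biased by a known amount or in a known direction.** No shift or slope is given, and every bias figure above rests on assumed inputs.
- **That later disclosure makes the ANCOVA estimate more accurate.** Its net error could fall or rise, with the break-even at about 25-40% persistence under the assumed slopes.
- **That changing the call alone secures a clean pretest.** That depends on the unstated timing of the PT steps.

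Stakes are limited because the between-group analyses are preliminary and unpowered. They are not nil, because the plan uses them, and the baseline values, to design a future trial.

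**What to change.** 1. **Notification:** the call gives only the date and time of the baseline visit.
2. **Baseline Data Collection and Orientation:** after questionnaires and tests are finished and the data collector has released the participants, unblinded staff disclose the arm and its session schedule at the existing handover. The schedule moves with the arm because the session counts differ (8 plus a booster against 6) and could hint at it.
3. **Both sections:** reword the instructions about not telling the data collector so that they apply to the 6-week, 3-month and 6-month visits.
4. **Statistical Analysis Plan:** state that follow-up self-reports come from participants who know their arm.
5. **Documentation of PT and OT Services:** state when the arm-specific registration and PT-discharge steps fall relative to baseline, and reconcile them with the disclosure point. No position is taken here on when PT stops.

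Randomization may still precede baseline, and the separate rooms or times can stay. The cost is wording, a changed call and the reconciliation in item 5, with no added visit, staff or measure. The downside is later notice of each participant's own schedule, with a possible slight effect on attendance and completion.

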## **Data Collection**

### **Feasibility Data**

We will use the eligibility form (Appendix G) to collect data on:

Number eligible

Number refusing.

We will collect number consenting from the consent forms

We will track class attendance using an attendance sign-in sheet (Appendix O)

Cancellations (notification) and no-show status will be tracked by the class instructor ([name] for Intervention and [name] for control).

Unanticipated problems must be reported to the BU IRB using the Reportable Events and New Information form. BU IRB requires that all Unanticipated Problems meeting the definition listed above and involving a fatal or life-threatening event be reported to them **within 2 days** of learning of the event. Unanticipated Problems not involving a fatal or life-threatening event must be reported to BU IRB **within 7 days** of learning of the event.

All Adverse Events and Serious Adverse Events that do NOT qualify as Unanticipated Problems must be reported to the BU IRB in section 5 of the Continuing Review submission and include the Principal Investigator's conclusion that the pattern of events does not suggest a greater risk of harm.

### **Adverse Event Recording from the Baseline Data Collection through Week 6 (in-person classes)**

Because this study includes older adults at increased risk for falls, we expect adverse events in this study to include falls. In addition, we expect adverse events from exercise in both groups to include: fatigue, muscle soreness or other discomfort or a fall or injury during tests and exercise. As per Lamb 2005, falls will be described as "unexpected events in which the participants come to rest on the ground, floor, or lower level." Participants will be provided with the definition of falls used in this study in the Baseline Data Collection & Orientation session (prior to starting the program). They will be provided with their binders, and we will instruct them in the use of the Action plan to record daily any falls or adverse events, symptoms and questions, as they occur. At each session, the instructor will collect the forms, make copies for study documentation, and return them to the participants.

If participants report fall(s) and/or adverse effects/events through the Action Plan (intervention) or Activity Tracker (control), or verbally, in-person or by telephone, the instructor will provide appropriate clinical assessment and recommendations and modifications if safe to continue participating in the program and document in the clinical flow chart. In addition, the instructor will fill out the Adverse Event Form (Appendix P) and provide the form to the research assistant, who will document the event in a master log of all adverse events.

If a participant falls or experiences an adverse event while attending the class session, the instructor will provide appropriate clinical assessment and recommendations and modifications if safe to continue participating in the program and document in the clinical flow chart. If injury occurred and the participant was unable to participate in the class, the instructor will complete and submit an RL Solutions event as per Mt Ascutney procedures. The instructor will determine

whether the participant needs to seek medical attention at MAHHC and assist the participant to the clinic or emergency department. In addition, the instructor will fill out the Adverse Event Form (appendix P) and provide the form to the research assistant for documentation in the master log.

If any adverse event, either self-reported or experienced during class, meets the definition of Unanticipated Problem, the instructor will, in addition to providing the Adverse Event Form to the research assistant, notify the principal investigator immediately (same day). The principal investigator will notify the Boston University IRB within 2 business days if the adverse event meets the definition of Unanticipated Problem and involves a fatal or life-threatening event, and within 7 days otherwise. All adverse events that do not meet the definition of Unanticipated Problem will be reported by the principal investigator to the Boston University IRB at the time of continuing review.

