### **Healthy YOUiversity**

The Healthy YOUiversity instructor ([name]) will conduct an orientation that will consist of an explanation of the overall structure of the class, the calendar, and provision of the participant binder, providing our definition for falls, documentation of their exercise, falls and adverse events, and how to contact study staff.

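### The study's fall definition is scheduled after the baseline fall questions, so baseline falls may be reported on each participant's own idea of a fall

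*Combined protocol and SAP*

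**What the plan says.** The protocol adopts one definition of falls, taken from a cited consensus paper: "unexpected events in which the participants come to rest on the ground, floor, or lower level". It stands in the section on adverse event recording from baseline through week 6. On timing, that section says "Participants will be provided with the definition of falls used in this study in the Baseline Data Collection & Orientation session", before the program begins.

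The table of baseline measures lists "Recent fall(s) and mobility questions" among the self-report items for both groups and refers to Appendix R for the form.

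The section on baseline data collection and orientation sets the order within the session: "When participants have completed the questionnaires and physical tests, The Data Collector ([name]) will release them to unblinded study staff", "who will bring the participants to the appropriate location for their separate orientation sessions". Before that release, the blinded data collector hands out the questionnaires and is available to explain items.

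The fall definition is then an item of each orientation. It is on the list under Orientation to the Program for the intervention group. For the control group, the Healthy YOUiversity orientation includes "providing our definition for falls, documentation of their exercise, falls and adverse events".

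The SAP says that baseline fall rates will be examined to support sample size calculations for a later trial. It also plans to explore how baseline characteristics relate to outcomes, and to summarise falls as counts and percentages under safety.

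**The concern.** People differ on what counts as a fall. Some may count a stumble caught on furniture, and some may leave out a slow slide to the floor. A fixed definition is meant to remove that variation, but it can do so only for questions answered after the participant has heard it.

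The main thing at stake is planning. The study is not powered to compare outcomes, so much of its value lies in what it passes on to a later trial. If the baseline fall rate is collected without the definition and the later trial counts falls with it, the planning rate and the planned endpoint may not match. Any reading of change in falls from baseline would carry the same mismatch, as would any use of baseline falls as an explanatory variable. Baseline reports cannot be cleanly collected again once participants have been taught the definition.

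**Working it through.** There is no plan figure to reproduce. The documents give no fall rate, no falls-based sample size and no misclassification rate. The check is of the order of events.

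1. **Are falls asked at baseline?** Yes, by self-report, in both groups (baseline measures table).
2. **When are they answered?** Before orientation. The release step comes only after the questionnaires and tests are complete: "When participants have completed the questionnaires and physical tests, The Data Collector" then hands participants over. This is written under the intervention group's subheading, but the paragraph covers scheduling for both groups and speaks of separate orientations.
3. **When is the definition given?** At orientation, in both arms (Orientation to the Program; Healthy YOUiversity).
4. **Does the week-6 adverse event section contradict this?** No. It places the definition in the combined session and before the program starts. Steps 2 and 3 satisfy that. The timing protects the daily records, which begin afterwards, but not the baseline questions.
5. **Does anything put the definition in front of participants earlier?** Not in the text available. The offer to explain items reaches only those who ask. The training section covers questionnaire administration without mentioning the fall definition. Appendix R could print it, but is not shown.
6. **How are follow-up falls collected?** By daily self-recording after orientation, with telephone calls every 2 weeks after week 6 and falls questions at 3 and 6 months. Participants have been given the definition by then. Whether the later forms and the call script repeat it (Appendices T, U and P) cannot be seen.
7. **Where do baseline falls enter the analysis?** In the planning of a formal trial, and in the exploration of baseline characteristics against outcomes. The SAP names no baseline-to-follow-up comparison of falls, only preliminary analyses of change in general.

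On scale, the only usable input is the planned 48 participants. If the baseline rate is expressed as the proportion with a recent fall, each participant whose status would differ under the definition moves it by 1/48 = 0.021, about 2.1 percentage points. This is the size of one step. The documents do not say how many steps there would be, and steps in opposite directions would cancel.

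**The case against.** The strongest reply is that the wording of the baseline items is unseen. If Appendix R prints the definition, the problem does not arise. That stands, and it limits the conclusion to what may happen. A reader might infer that baseline and follow-up falls are in fact counted on different definitions. The documents do not show this, because the forms at both ends are missing from the text.

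A second reply is that little depends on it. Falls are summarised descriptively, the study is unpowered, and no before-after test of falls is named. This stands in part: it leaves the planning use of the baseline rate, which the SAP states explicitly.

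A third reply is that a shared definition would not make the two sets of falls comparable, since baseline falls are recalled and follow-up falls are recorded daily and by telephone. This is correct. A common definition is needed for comparability but does not suffice.

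A reader might also infer that, because each arm hears the definition from its own instructor, fall counting will drift apart between arms. The documents do not support that. There is one written definition, all research staff attend common training that covers data collection and adverse event reporting, and a blinded assessor makes the calls after week 6 from a standard script. Nothing suggests that the two instructors would teach it differently.

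**Conclusion.** The point holds in a limited form. As the procedure is written, participants answer the baseline fall questions before they are given the study's definition, and the text does not say that those questions carry it. Baseline falls may therefore be reported on personal definitions. This weakens the baseline fall rate as a planning input and any before-after reading of falls. It does not by itself bias the between-arm comparison of follow-up falls, because the order is the same in both arms.

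The size cannot be derived from the documents, and the direction is unknown. The conclusion rests on two assumptions: that Appendix R does not already contain the definition, and that the SAP's baseline fall rates are drawn, at least in part, from the recent-falls questions. If the first is wrong, the point is met. If the second is wrong, what remains is the use of baseline falls as a baseline characteristic and in any assessment of change.

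**What to change.** First check Appendices R, T and U. If they already carry the definition, say so in the baseline data collection section, and nothing more is needed.

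If they do not, make two changes before enrolment:

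- Have the blinded data collector give the protocol's definition, in fixed wording, to every participant before the baseline fall questions. The definition contains nothing about assignment, so blinding is unaffected. Orientation then only repeats it.
- Print the same wording above the fall items on the baseline, 3-month and 6-month forms.

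The cost is one existing sentence moved earlier and printed on existing forms, with no added visits or staff. The difference between recalled and daily-recorded falls will remain, and should be stated wherever baseline and follow-up falls are set side by side.
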